The Danish National Prescription Registry on use of anti-reflux medication (ATC: A02BA, A02BC, A02BX), anti-thrombotic treatment (ATC: B01A), non-steroid anti-inflammatory drugs (NSAID) (ATC: M01A) and selective serotonin reuptake inhibitors (SSRI) (ATC: N06AB) in a time period beginning two years before surgery and ending at end of follow-up. The Danish National Prescription Registry contains information on all sale of prescription drugs including date of sale, Anatomical Therapeutic Chemical Classification (ATC) code, civil registration number of buyer and package volume since 1994 (53).

Statistics Denmark on educational level at time of primary surgery (54) defined by ISCED (55), occupation status (employed/unemployed/retired) (56) and equivalent annual income in the year preceding primary surgery (57).

Primary outcome

Primary outcome of the study is treatment success or failure, with failure defined for each patient as at least one of the following statements being fulfilled:

1. Having undergone reoperation (NSCP: KJBC00-02, KJBW96-98, KJBB00-01, KJBB96-97) between index date and end of follow-up.
2. Having filled prescription of >60 DDD/year of PPI in any year between index date and end of follow-up.
3. Having no measure ≥ 3 on GERD-HRQL indicating symptoms being bothersome every day.
4. Having no measure ≥ 4 on Dysphagia Handicap index indicating symptoms being a moderate problem.

Date of failure will be defined as follows: In case of 1), date of failure will be date of reoperation. In case of 2), date of failure will be date of first prescription filled in the year, where >60 DDD of PPI are filled. In case of 3) or 4), date of failure will be end of follow-up.

Secondary outcomes

Secondary outcome will be 90-day mortality after primary surgery, rate of reoperation, use of PPI in DDD/year, use of PPI at follow-up (including indication and prescribing physician) and Quality of life defined by GERD_HRQL, Dysphagia Handicap Index.

Statistical analysis

Contingency tables

Contingency tables will be created listing:

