Cox regression will be performed with treatment success as dependent variable, time to end of follow-up (as defined above) and the following variables will be tested and included as independent variables where appropriate: Age (median), sex (male/female), body mass index (kg/m²), alcohol consumption (drinks of 12g ethanol per week), tobacco use (current, former or never-smoker), ASA-score, CCI, preoperative psychiatric diagnoses, use of anti-reflux medication (yes/no), NSAID (yes/no) and SSRI before surgery (yes/no) and previous abdominal surgery (yes/no), educational level at time of primary surgery (ISCED), occupation status (employed/unemployed/retired) and equivalent annual income in the year preceding primary surgery, typical symptoms (yes/no), atypical symptoms (yes/no) and dysphagia (yes/no), endoscopically verified occurrence of hiatal hernia (yes/no), esophagitis (yes/no), measures from 24-hour pH-measurement and esophageal manometry: reflux-index (%), symptom correlation (%) and presence of esophageal motility disorder (hypomotility, normal motility or hypermotility), type of fundoplication (270° Toupet/360° Nissen).

Clinical scoring system

Using results from the Cox regression and using the methods for validation described by Steyerberg et al (58), a clinical scoring system will be developed with the purpose of identifying probability of treatment success based on preoperative known variables.

Dataflow

Data collected from electronic patient records and patient-reported quality of life follow-up will be stored using RedCAP (REDCap 7.4.23, Vanderbilt University, Nashville, TN, USA) hosted by OPEN - Odense Patient Data Explorative Network, Department of Clinical Research, University of Southern Denmark and Odense University Hospital, Denmark. Data will be transferred to Statistics Denmark and merged with registry-data. All analysis will be performed using STATA15 (StataCorp, College Station, TX, USA) on the servers of Statistics Denmark.

Ethics and dissemination

The study has been approved and registered at Lillebaelt Hospital according to current Danish Law and has previously been approved by The Danish Data Protection Agency (Permission #17/1942). Generated datasets will be stored on the servers of Statistics Denmark in compliance with Danish and EU-regulations

on personal health data and will be anonymized after merging, so that the unique personal identifier is removed.

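### Two of the four criteria for treatment failure are worded backwards, so a symptom-free patient counts as a failure

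*Combined protocol and SAP*

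**What the plan says.** The Primary outcome section sets a two-way outcome, success or failure, "with failure defined for each patient as at least one of the following statements being fulfilled". Four numbered statements follow. The first is a reoperation, identified by a list of procedure codes, at any time from surgery until follow-up ends. The second is PPI dispensing above 60 DDD in at least one year over the same span.

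The third concerns reflux symptoms on the questionnaire: "Having no measure ≥ 3 on GERD-HRQL indicating symptoms being bothersome every day". The fourth takes the same form for swallowing symptoms, with its own instrument and cut-off: "Having no measure ≥ 4 on Dysphagia Handicap index indicating symptoms being a moderate problem".

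The section then dates each kind of failure. For the two questionnaire criteria the rule is "In case of 3) or 4), date of failure will be end of follow-up". Success has no definition of its own, so it is whatever is left when no statement applies.

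The Cox regression section uses this outcome: "Cox regression will be performed with treatment success as dependent variable". The Clinical scoring system section builds the score on the Cox results, to give the probability of success from variables known before surgery.

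**The concern.** Statements 1 and 2 become true when something has gone wrong. Statements 3 and 4 become true when nothing has gone wrong, because each requires that no measure reaches a threshold which the same sentence explains as troublesome or moderate symptoms. They read like conditions for success placed in a list of conditions for failure.

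Because any one statement is enough, the effect goes beyond a sign error on two items. The absence of either symptom, on its own, makes the patient a failure. The best result the operation can give is classed as failure, and success requires two bad symptoms together.

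This is the primary endpoint, and both planned papers rest on it. No other section restates the rule in the opposite direction.

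**Working it through.** The plan states no expected failure rate, sample size or power, so there is no figure to reproduce. The check is one of logic, followed by an illustration of size.

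**Step 1: the two rules.** Write R for reoperation, P for PPI above 60 DDD in any year, G for at least one GERD-HRQL measure of 3 or more, and D for at least one Dysphagia Handicap Index measure of 4 or more.

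- As written: failure = R or P or not-G or not-D. Success therefore requires not-R, not-P, G and D.
- With 3 and 4 turned round: failure = R or P or G or D. Success requires not-R, not-P, not-G and not-D.

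**Step 2: all combinations.** There are 2 × 2 × 2 × 2 = 16 profiles. Each rule makes 15 of them failures and 1 a success, but not the same one. In the 12 profiles with R or P, both rules give failure. The other four are:

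| Profile (no R, no P) | As written | Turned round |
|---|---|---|
| Neither symptom | Failure | Success |
| Dysphagia only | Failure | Failure |
| Reflux only | Failure | Failure |
| Both symptoms | Success | Failure |

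The rules disagree in two profiles, the symptom-free patient and the patient with both symptoms, and they swap them exactly.

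**Step 3: size on symptoms alone.** The prevalences of G and D at follow-up are assumptions, because the documents give none. Take G = 20% and D = 15%.

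- Independent symptoms. As written: 1 − 0.20 × 0.15 = 0.97. Turned round: 1 − 0.80 × 0.85 = 0.32.
- Maximum overlap. As written: 1 − min(0.20, 0.15) = 0.85. Turned round: max(0.20, 0.15) = 0.20.

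Over G from 10% to 30% and D from 10% to 20%:

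| Dependence | Failure as written | Failure turned round |
|---|---|---|
| Independent | 94% to 99% | 19% to 44% |
| Maximum overlap | 80% to 90% | 10% to 30% |

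For example, with independence, 1 − 0.30 × 0.20 = 0.94 and 1 − 0.10 × 0.10 = 0.99; turned round, 1 − 0.90 × 0.90 = 0.19 and 1 − 0.70 × 0.80 = 0.44.

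**Step 4: size for the whole endpoint.** Study population gives 557 operated patients. Suppose that all take part, that 41.1% meet criterion 1 or 2, and that this is unrelated to symptoms. The 41.1% is borrowed from the 10-year risk of long-term PPI use in Background, which is not the same definition as criterion 2. Then 557 × (1 − 0.411) = 328 patients are classified by symptoms alone.

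| G / D, independent | Successes as written | Successes turned round |
|---|---|---|
| 10% / 5% | 328 × 0.005 = 2 | 328 × 0.855 = 281 |
| 20% / 15% | 328 × 0.03 = 10 | 328 × 0.68 = 223 |
| 30% / 20% | 328 × 0.06 = 20 | 328 × 0.56 = 184 |
| 50% / 30% | 328 × 0.15 = 49 | 328 × 0.35 = 115 |

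(Products use the unrounded 328.07.) At 20% / 15% with maximum overlap the counts are 328 × 0.15 = 49 and 328 × 0.80 = 262.

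The Cox regression section lists 24 candidate variables. In most of these scenarios the literal rule leaves fewer successes than variables.

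**The case against.** The best reply is that the intended direction is obvious. The explanations attached to the thresholds, the direction of criteria 1 and 2, and the aim of better patient selection all point one way. A dataset in which nearly every symptom-free patient was labelled a failure would be noticed at once, and the documents do not show how the outcome will be coded. On this view it is a drafting slip with little practical risk.

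Several parts of that reply stand:

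- The analysts may well code the intended direction. The harm described here follows only if the text is applied literally.
- The endpoint is not reversed as a whole. Criteria 1 and 2 are sound, and patients with exactly one symptom are failures under either rule. Only two of the 16 profiles change.
- The symptom prevalences are assumed, and the percentages in Step 3 leave out patients who already fail on reoperation or PPI, for whom the wording changes nothing.
- The date rule for criteria 3 and 4 refers to them by number only. It confirms that they count as failure events but says nothing about direction.
- It has not been shown that a score built on the literal rule would favour patients with poor results. The more direct consequence is an outcome with very few successes, placed in the wrong patients.

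None of this removes the point. The text is the pre-specified definition of the primary outcome, and one of the two profiles that change is the very patient whom surgery is meant to produce. If the direction is reversed silently once data have been seen, a reader cannot tell a corrected slip from an endpoint changed after the fact.

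**Conclusion.** The concern holds. That criteria 3 and 4 run the wrong way follows from the plan's own wording and needs no outside knowledge of the two questionnaires and no assumption about prevalence. Read literally, the rule gives a wrong classification for every patient who is clear of reoperation and excess PPI and has either both symptoms or neither.

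The size depends on assumed prevalences and on how far the symptoms overlap. In every scenario examined the gap is large, although it narrows as symptoms become more common. That the two lines began as success criteria is inference, and the investigators should confirm it. The correction must be made before the outcome is derived.

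**What to change.** In the Primary outcome section, restate the two criteria so that they run the same way as the first two:

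- Criterion 3: at least one GERD-HRQL measure of 3 or more.
- Criterion 4: at least one Dysphagia Handicap Index measure of 4 or more.

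Add one sentence defining success as none of criteria 1 to 4 being met. This already follows from the two-way outcome, but stating it would expose any remaining contradiction. An equivalent repair keeps the present wording of 3 and 4 but moves it into a definition of success in which all conditions must hold together.

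The investigators should confirm the intended direction, record the change with a date, and check that the code deriving the outcome matches. The cost is a few words and a short code check, with no new data and no change to the analysis methods.

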Laparoscopic anti-reflux surgery is more effective than medical management with regard to short to medium length follow-up (12,34,35). Few studies provide long-term follow-up. After ten years, the benefits of surgery seem to decrease, but there is still a significant improvement in quality of life compared to preoperative measurements (36,39). Known causes of dissatisfaction are postoperative complication, redo-fundoplication and developing new bothersome symptoms such as gas-bloat and dysphagia combined with inadequate symptom relief (37,40).

Follow-up of randomized clinical trials have demonstrated, that anti-reflux surgery patients use acid suppressing drugs, primarily proton pump inhibitor (PPI) therapy at postoperative follow-up. Use have been considered minimal with <20% using PPI-therapy (35) and 27-44% using PPI at five-year follow-up (38). A recent register-based study (41), demonstrated a greater number of redeemed prescriptions of proton

pump inhibitor after primary anti-reflux surgery, than previously known. Five-, 10- and 15-year risks of long-term PPI use were 29.4%, 41.1% and 56.6%. However, this register-based study could not examine whether patients had objective recurrence of reflux disease and also did not examine indication for treatment as well as prescribing physician. From 2001 to 2011, 94.4% of PPI where prescribed in primary care (42) and it is unknown why post-fundoplication patients are prescribed PPI. It has previously been demonstrated, that the use of acid suppressing drugs after anti-reflux surgery does not necessarily correlate with abnormal acid exposure to the esophagus (43,44). In general, the use of PPI has increased rapidly in Denmark, rising 243% from 2001 to 2011 despite more restrictive guidelines and changes in reimbursement (42). As the majority of proton pump inhibitors are prescribed by general practitioners and not by the surgical centers, surgeons have very little knowledge of this aspect of life following anti-reflux surgery.

This study is part of the PhD project entitled: "Utilization, outcome and development of laparoscopic anti-reflux surgery" originating from the University of Southern Denmark (Protokol #: SDUSF-2016-115-(682)).

Methods and analysis

The study is a retrospective cohort study utilizing data from patient records and follow-up with patient-reported quality of life as well as registry-based data.

Study population

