The study population consists of all adult patients (age ≥ 18) having undergone laparoscopic anti-reflux surgery (Nomesco Classification of Surgical Procedures (NCSP) (45): KJBC01) from January 1, 2002 to December 31, 2013 in The Department of Surgery, Kolding Hospital, a part of Lillebaelt Hospital Denmark (n=557). Patients will be identified through Lillebaelt Hospital's Patient Administrative System. Day of surgery will be considered index date.

Date of follow-up will be the date, patient filled out quality of life questionnaires as described below. For patients deceased since index date, permission to include data from electronic patient records and registry-based data will be applied for from The Danish Patient Safety Authority.

All patients will be contacted by the existing Danish national digital communication system (e-Boks) and asked to participate in the study. Patients exempt from using the system, will be contacted by letter. Only patients providing informed consent will be included in the study.

Data sources

Data for the study will consist of electronic patient records, follow-up with patient-reported quality of life measurements and registry-based data.

Electronic patient records

From the electronic patient records, the following data will be identified: age (years), sex (male/female), body mass index (kg/m^2), alcohol consumption (drinks of 12g ethanol per week), tobacco use (current, former or never-smoker), ASA-score, Charlson Comorbidity Index (CCI) (46) and previous abdominal surgery (yes/no).

Preoperative endoscopically verified occurrence of hiatal hernia (yes/no), esophagitis (yes/no) will be included as well as, from 24-hour pH-measurement and esophageal manometry, reflux-index (%), symptom correlation (%) and presence of esophageal motility disorder (hypomotility, normal motility or hypermotility). Patients preoperative reflux symptoms defined as typical symptoms (yes/no), atypical symptoms (yes/no) and dysphagia (yes/no) are included as are surgical data included duration of surgery (minutes), type of fundoplication (270° Toupet/360° Nissen), Length of hospital stay (days), per- and postoperative complications registered within 30 days as defined by Clavien-Dindo (47).

Quality of life follow-up

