Patients will be contacted as described above and asked to answer validated questionnaires regarding disease-specific quality of life (GERD-HRQL) (48) and dysphagia (Dysphagia Handicap Index) (49). Patients will also be asked if they are currently taking PPI (yes/no), in what dosage (never/when needed/once daily/twice daily), which symptoms have warranted PPI-use (reflux symptoms/dysphagia/gastritis/preemptive against peptic ulcer disease/other) and which physician prescribed the drug (general practitioner/surgeon/other doctor at hospital/other specialist in private practice)

Registries

All Danish inhabitant are issued with a civil registry number at birth or at date of moving to Denmark. The civil registry number are a unique personal identifier and is used across a variety of nationwide databases with regards to health, financial and educational data. Data from the following nationwide Danish registries will be included in the study:

The National Patient Registry (NPR) on re-operative surgery (NCSP: KJBC00-02, KJBW96-98, KJBB00-01, KJBB96-97) and endoscopy (NCSP: KUJD02-05, KJCA55) during follow-up). NPR contains records of all discharge diagnosis since 1977 and all outpatient diagnosis since 1994 (50,51). All performed procedures, including endoscopies and surgeries are also registered using NCSP.

The National Patient Registry of Psychiatry (NPR-PSYK) on psychiatric diagnoses (ICD-10: F01-F99) in a two-year period before primary surgery. NPR-PSYK is a sub-registry of NPR and specifically contains records of all psychiatric discharge and outpatient diagnosis from psychiatric departments since 1995 (50,51).

The Civil Registry on marital status, 90-day mortality after primary surgery and all-cause mortality during follow-up. The Danish Civil Registry maintains complete records of births, deaths, civic status and emigration status of the entire Danish population based on civil registration number (52).

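### Dating symptom-only failures on the questionnaire day makes Cox-based success probabilities too high early and too low towards maximum follow-up, by an amount the documents do not fix

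*Combined protocol and SAP*

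**What the plan says.** The combined protocol and SAP defines failure by four criteria. Reoperation (criterion 1) and PPI prescriptions (criterion 2) carry registry dates. For the questionnaire criteria the Primary outcome section says "In case of 3) or 4), date of failure will be end of follow-up". Under Study population, "Date of follow-up will be the date, patient filled out quality of life questionnaires as described below"; one postoperative questionnaire is described. Operations run "from January 1, 2002 to December 31, 2013", with surgery as time zero.

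The Cox regression section says "Cox regression will be performed with treatment success as dependent variable, time to end of follow-up (as defined above", closing the bracket there. From its results "a clinical scoring system will be developed with the purpose of identifying probability of treatment success based on preoperative known variables". No horizon, interval-censored or current-status method, or sensitivity analysis for this dating is given.

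Two points in the text must be settled first:

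- Criterion 3 is printed as "Having no measure ≥ 3 on GERD-HRQL indicating symptoms being bothersome every day", and criterion 4 has the same form. Taken literally, patients without bothersome symptoms fail. I read both as intended, with a score at or above the cut-off as failure. On the printed text the sizes below do not apply.
- The time variable in the Cox section can mean the failure dates under Primary outcome, or the questionnaire date for everyone. The second would discard the reoperation and prescription dates too. I use the first.

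**The concern.** For a patient who fails on criterion 3 or 4 alone, the data show that symptoms were present on one day. When they began is unknown. The plan treats that day as an exact event time and mixes it with true registry dates.

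Follow-up length is set by the operation date. No symptom-only failure can therefore be counted before the shortest follow-up, and later ones are counted late, against a shrinking risk set. Any probability of success read from the model at a stated time is affected, and such a probability is what the score is meant to provide. A score used only to rank patients is exposed only through the hazard ratios.

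**Working it through.** The plan states no success curve or event count, so there is no figure to reproduce.

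**Inputs from the documents.** The 12-year operation window, the dating rule, and as a proxy for registry failure the Background figures "Five-, 10- and 15-year risks of long-term PPI use were 29.4%, 41.1% and 56.6" per cent (long-term PPI use, which is not criterion 2's definition).

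**Assumptions.** Even surgical volume; survey date 2017.5–2019.5; symptom onset 0.5–2.3% per year (5–21% by 10 years); symptom and registry failures independent; 334 responders (60% of 557). A registry failure rate of 3% per year is the alternative to the proxy.

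**1. Formula.** Let b be maximum follow-up, R(t) the proportion free of registry failure, and q(u) the proportion of those with symptoms at u years. In large samples:

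- Plan: S(t) = R(t) × exp(−∫ q(u)/(b−u) du), integrated from b−12 to t.
- Target: R(t) × (1 − q(t)).

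Before b−12 the integral is zero, so the plan is too high by R(t)q(t). As t approaches b the integral grows without limit and the plan's curve falls to zero, so it ends too low. Uneven volume changes the weights but neither end result.

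**2. Constant prevalence, no persistence (q = 10%, survey 2018.5, b = 16.5).** The plan removes 1 − ((16.5−t)/12)^0.1 of registry-free patients: 0.4% at 5 years, 5.9% at 10 and 18.8% at 15. The target is 10% throughout.

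**3. Persistent symptoms (q = 1 − exp(−0.023u), b = 16.5, registry proxy).** The integral is 0.0044, 0.0971 and 0.4778 at 5, 10 and 15 years.

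| Years | Plan | Target | Error |
|---|---|---|---|
| 5 | 70.6 × exp(−0.0044) = 70.3% | 70.6 × exp(−0.115) = 62.9% | +7.4 |
| 10 | 58.9 × exp(−0.0971) = 53.4% | 58.9 × exp(−0.23) = 46.8% | +6.6 |
| 15 | 43.4 × exp(−0.4778) = 26.9% | 43.4 × exp(−0.345) = 30.7% | −3.8 |

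Simulated cohorts of 334 give 70.3, 53.5 and 26.9%. A Cox model with predicted success shows the same pattern.

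**4. Ranges (points, even volume, both registry patterns).** Survey 2017.5–2019.5, except the front-loaded row (2018.5).

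| Symptom pattern | 5 years | 10 years |
|---|---|---|
| Persistent, 0.5% per year | +1.5 to +2.1 | +1.3 to +2.2 |
| Persistent, 0.5–2.3% per year | +1.5 to +9.4 | +1.3 to +9.6 |
| Persistent, front-loaded, 21% by 10 years | +10.2 to +12.4 | +5.9 to +7.4 |
| Constant prevalence 5–20% | +3.1 to +17.2 | +0.6 to +8.2 |

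**5. Where the sign turns.** With a constant fraction p the curves cross 12 × (1−p)^(1/p) years before b: 4.18 years for p = 0.1 and 3.00 for p = 0.5. Across onset patterns the range is about 1.75–4.2 years with even volume, and about 1.35–6.9 if volume fell or rose strongly. If volume rose linearly from zero, the integral doubles. At 10 years the case in step 3 becomes 58.9 × exp(−0.1943) = 48.5%, an error of +1.7. With survey 2017.5 (even-volume integral 0.118) it is 58.9 × exp(−0.236) = 46.5%, an error of −0.3.

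**6. Hazard ratios (simulated).**

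- Equal effect on both failure types (HR 2): 1.95 against 1.99 with true onset dates, and 1.93 against 2.00.
- Null predictor unrelated to operation year: 1.00, with 4.6–5.8% false positives.
- Null predictor whose prevalence moves from 20 to 80% over the window, at 2.3% per year: 1.12–1.23, with 11.5–23.1% false positives. Adding operation year brings this to 1.00–1.01.
- Predictor doubling symptom onset only, at 2.3% per year: 1.16 instead of 1.29, and 1.28 instead of 1.44. Operation year does not help here.

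**The case against.** **Criteria 3 and 4 may mean status at follow-up.** Criteria 1 and 2 name an interval from surgery; 3 and 4 do not. Persistence and a true onset date are then the reviewer's additions. This is a fair reading, and the questionnaire day would suit a binary outcome. It does not rescue an exact event time in a Cox model: step 2 assumes no persistence and finds the same pattern. If prevalence varies as symptoms come and go, one questionnaire cannot identify the onset curve, and its error cannot be sized.

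**A reader might infer that success is understated in about the last 3 years, or always at 15 years.** The documents support neither. They give no annual volumes and no survey date. The crossing moves as in step 5, and with even volume and a survey at 2020.5 the 15-year error turns slightly positive (up to about 3 points). The largest negative 15-year errors, −10.6 and −15.1 for survey 2017.5, also rest on almost nobody: 334 × 0.434 × 0.5/12 ≈ 6 patients at risk, or 334 × 0.638 × 0.5/12 ≈ 9 at 3% per year.

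**A reader might also infer that the predictors are generally distorted.** That needs drift with operation year or an effect on symptoms alone, and the documents show neither. Equal effects are plausible, since patients are asked "which symptoms have warranted PPI-use (reflux symptoms/dysphagia/gastritis/preemptive against peptic ulcer disease/other": the same symptoms can lead to PPI use. A 20-to-80% drift is extreme.

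**The gain may be small.** At 0.5% per year the error is about 2 points at 5 and 10 years. This stands.

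**Conclusion.** The concern holds under the two stated readings. The early overstatement and late understatement follow from the dating rule and the staggered operation dates, both for persistent symptoms and for constant prevalence. The sizes in step 4 are conditional on even volume, the assumed survey dates and the assumed symptom and registry rates. With rising volume the 10-year error can be near zero. The mechanism is certain and its size is not, so this should be changed before analysis; it is not a reason to doubt every hazard ratio.

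**What to change.** 1. Reconcile the Primary outcome and Cox regression sections: criteria 1 and 2 use their registry dates, with censoring at the questionnaire. Correct the wording of criteria 3 and 4 separately.
2. Do not use the questionnaire day as an exact event time for failures on 3 or 4 alone. Choose one of:
   - Two parts. Cox for criteria 1 and 2 with operation year as a covariate, held at a reference value when the score is applied. Then, among patients free of criteria 1 and 2 at the questionnaire, complementary log-log regression of symptom status on log time since surgery and a small prespecified set of predictors. Success at t is registry-free by t and symptom-free at t, the product of the two parts. This definition does not require persistence.
   - Interval censoring between surgery and questionnaire, in a proportional hazards model with a flexible baseline and the persistence assumption stated.
3. If the single Cox model is kept, add operation year and report one of these as a sensitivity analysis. Operation year removes drift bias only.
4. Report success at fixed horizons within observed follow-up where enough patients remain at risk.

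In simulation the two-part curve was biased by −0.8 to +0.4 points at 5, 10 and 15 years. The interval-censored model was biased at 5 years by +0.1 to +2.1 with constant-rate onset, and by +4.2 to +4.7 with front-loaded or non-persistent symptoms. These checks cover overall curves, not a score with many predictors.

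**Cost.** No new data, but more than a change of wording. Expected symptom-only events among 334 patients are 334 times the average of R(u)q(u) over follow-up: about 9–13 at 0.5% per year and 36–53 at 2.3%. The Cox section lists 24 candidate predictors, so the symptom part needs a short or penalised list. With one survey date it cannot separate operation year from time since surgery.

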- 1) Patient characteristics: Age (median), sex (male/female), body mass index (kg/m^2), alcohol consumption (drinks of 12g ethanol per week), tobacco use (current, former or never-smoker), ASA-score, CCI, preoperative psychiatric diagnoses, use of anti-reflux medication (yes/no), NSAID (yes/no) and SSRI before surgery (yes/no) and previous abdominal surgery (yes/no), educational level at time of primary surgery (ISCED), occupation status (employed/unemployed/retired) and equivalent annual income in the year preceding primary surgery.
- 2) GERD characteristics: Symptom profile: typical symptoms (yes/no), atypical symptoms (yes/no) and dysphagia (yes/no), endoscopically verified occurrence of hiatal hernia (yes/no), esophagitis (yes/no), measures from 24-hour pH-measurement and esophageal manometry: reflux-index (%), symptom correlation (%) and presence of esophageal motility disorder (hypomotility, normal motility or hypermotility).

- 3) Operative characteristics: Duration of surgery (minutes), type of fundoplication (270° Toupet/360° Nissen), length of hospital stay (days), per- and postoperative complications registered within 30 days as defined by Clavien-Dindo and 90-day mortality.
- 4) Follow-up: Rate of reoperation (%), use of PPI in DDD/year, use of PPI at follow-up (including indication and prescribing physician), GERD-HRQL and Dysphagia Handicap Index.

Categorical and continuous variables will be compared using Chi², Fisher's Exact Test and Kruskal-Wallis-test where appropriate.

Cox regression

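### Reoperation, a named secondary outcome, is summarised only as a crude percentage over follow-up differing by up to about 12 years, so it has no time horizon and untimed group comparisons of it can be distorted

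*Combined protocol and SAP*

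**What the plan says.** The Study population section covers operations "from January 1, 2002 to December 31, 2013" and identifies 557 patients before consent. "Day of surgery will be considered index date", and "Date of follow-up will be the date, patient filled out quality of life questionnaires as described below". There is no fixed length of follow-up. Patients who have died may be included with the authority's permission, but no end of follow-up is defined for them.

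The Secondary outcomes section reads "Secondary outcome will be 90-day mortality after primary surgery, rate of reoperation, use of PPI in DDD/year", with no time point for reoperation. Under Contingency tables, item 4, the summary is "Rate of reoperation (%), use of PPI in DDD/year". One sentence gives the tests for all four tables: "Categorical and continuous variables will be compared using Chi², Fisher's Exact Test and Kruskal-Wallis-test where appropriate". The groups to be compared are not named.

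The only time-to-event analysis is the Cox regression for composite treatment success. The Primary outcome section dates a failure by reoperation at the operation itself, and the Registries section obtains mortality from the Civil Registry. Both dates should therefore be available. Year of surgery is not listed in the tables or among the Cox covariates.

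**The concern.** A percentage reoperated has a plain meaning when everyone has been observed for the same time. Here a patient operated on in early 2002 has had about 12 years longer to be reoperated than one operated on in late 2013. The crude figure averages risks over whatever follow-up the included patients happen to have. It cannot be set against a 5- or 10-year risk from another series, and it does not separate early from late reoperation. The plan's own Background shows why this matters: for long-term PPI use after this surgery it cites risks of 29.4%, 41.1% and 56.6% at 5, 10 and 15 years, which no single percentage would convey.

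The second issue is testing. Chi² and Fisher's test treat all patients as equally observed. If two groups differ in when they were operated on, a difference in crude reoperation can arise from length of follow-up alone.

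**Working it through.** The plan states no reoperation rate, sample size calculation or power, so there is no figure of its own to reproduce.

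**Spread of follow-up.** From 1 January 2002 to 31 December 2013 is 12.0 years. The questionnaire date is not given. If all patients answer in mid-2018 (assumption), follow-up runs from 4.5 to 16.5 years. For mid-2017 it is 3.5 to 15.5, and for mid-2019 it is 5.5 to 17.5. The spread is 12 years each time.

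**What the crude figure averages.** Assume a 10-year risk of 10%, a constant hazard, no deaths and surgery dates spread evenly.
- Hazard: h = −ln(1 − 0.10)/10 = 0.01054 per year.
- Risk at the shortest follow-up: 1 − exp(−0.01054 × 4.5) = 4.6%.
- Risk at the longest: 1 − exp(−0.01054 × 16.5) = 16.0%.
- Expected crude percentage, averaging over 4.5 to 16.5 years: 1 − [exp(−4.5h) − exp(−16.5h)]/(12h) = 10.4%.
- By the same formula, patients operated on in the first six years average 13.2% and those in the last six 7.6%.

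**Effect on a comparison with no true difference.** Take two near-equal groups (278 and 279) with the same hazard, where 75% of one and 25% of the other were operated on in the first six years.
- Expected crude percentages: 0.75 × 13.2 + 0.25 × 7.6 = 11.8%, and 0.25 × 13.2 + 0.75 × 7.6 = 9.0%.
- Standard error: √[0.104 × 0.896 × (1/278 + 1/279)] = 0.0259.
- Standardised difference: 0.028/0.0259 = 1.08.
- Rejection probability: about Φ(1.08 − 1.96) = Φ(−0.88) = 0.19. Simulation gives 19.6%.
- With 60% participation (assumption; 334 patients, 167 per group) the standard error is 0.0334 and the rejection probability is about Φ(0.84 − 1.96) = 0.13.

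**Range over the unknowns.** Simulation with 4,000 runs per scenario, 557 patients, mid-2018 questionnaire date and no deaths. Entries are rejection rates (%) of a two-sided 5% Chi² test under no true difference. The last two columns are for 10-year risks of 5 / 10 / 15%.

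| Timing of reoperations | Groups unrelated to year of surgery | 75/25 imbalance | Complete early/late separation |
|---|---|---|---|
| Constant hazard | 4.5 to 5.3 | 12.4 / 19.6 / 26.7 | 33.4 / 58.7 / 78.6 |
| Decreasing hazard (Weibull, shape 0.5) | 4.3 to 4.8 | 6.5 / 7.6 / 10.4 | 12.3 / 19.7 / 27.5 |
| All within 2 years | 4.7 to 5.2 | 4.9 / 5.2 / 4.0 | 4.9 / 5.7 / 5.0 |

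The simulation error near 5% is √(0.05 × 0.95/4000) = 0.34 points. A log-rank test on the same data rejects in 4.1% to 5.6% of runs across all 27 scenarios.

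**The case against.** A reader might infer that the plan's reoperation comparisons are already confounded by year of surgery, or that any characteristic that changed over 2002 to 2013 will appear related to reoperation. The documents do not support that. They name no groups for the tables, report no trend in fundoplication type or case mix, and say nothing about when reoperations occur. The test sentence covers every table variable, is qualified as applying where suitable, and does not specify a Chi² test of reoperation. If groups are unrelated to year of surgery, or all reoperations are early, the error rate stays near 5%. All of this stands, and it makes the testing half of the point conditional.

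It is also fair that time is not ignored everywhere. Reoperation enters the composite with its own date and so contributes to the Cox model, which is the plan's analysis of predictors. The crude percentage does not drive the primary analysis or the scoring system. But a composite that can also fail on PPI use or questionnaire scores gives no reoperation risk, so the secondary outcome remains without a timed estimate.

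Nor is the percentage without any meaning: it is the proportion reoperated between surgery and end of follow-up, and median follow-up would help in reading it. It would still not be a risk at a stated time.

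Finally, one might assume that follow-up of deceased patients stops at death. The plan does not say so; their end of follow-up is undefined.

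**Conclusion.** The point holds for estimation without any assumption about reoperation timing: a named secondary outcome has no time horizon although time at risk differs by up to about 12 years. With a constant hazard and a 10% ten-year risk, the single figure of 10.4% would average risks from 4.6% to 16.0%.

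For group comparisons it is a risk, not an established bias. It needs both an imbalance in year of surgery and reoperations continuing past the shortest follow-up. The reoperation risk, hazard shape, questionnaire date, imbalance and absence of deaths are all assumptions. The rates in the table use all 557 identified patients; with fewer participants the inflation is smaller. Since the timing is not known in advance and a time-to-event comparison keeps its error rate in every case examined, the change should be made. It concerns a secondary outcome and leaves the primary analysis untouched.

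**What to change.** - Report the cumulative incidence of first reoperation at 5 and 10 years with 95% confidence intervals, with death as a competing event (Aalen-Johansen). Under the mid-2018 assumption, (16.5 − 5)/12 = 96% of patients would have potential follow-up to 5 years and (16.5 − 10)/12 = 54% to 10 years, so both horizons are supported.
- Define the end of follow-up for deceased patients.
- Make any group comparison of reoperation with a time-to-event method instead of Chi² or Fisher, for example a cause-specific Cox model, and name the groups. That model compares hazards among patients still at risk, which is a different quantity from the cumulative incidence; the plan should say so.
- Give median follow-up and the crude count alongside.

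The cost is a wording change and slightly more analysis, using dates the study already plans to obtain. One limit remains. Living patients enter only by consent, while deceased patients may enter by authority permission. If participation is incomplete, deaths will be over-represented, so the estimate describes the included patients and not necessarily the whole operated cohort. The report should state this.
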